3 INTRODUCTION

This SAP has been developed to supplement the statistical analysis described in the clinical study protocol (final version dated 25 April 2013).

This SAP describes the methodology and considerations of the planned analyses and a list of all the TFLs for this study. A detailed description of the planned TFLs will be provided in a separate TFLs shell document. Any changes to the TFL shells numbering or to the title of the TFLs will not require an amendment to this SAP.

This SAP and any amendments will be finalized prior to the lock of the clinical database. Any changes to the analyses described in this document or additional analyses performed to supplement the planned analyses, will be described in the clinical study report (CSR).

The preparation of this SAP is based on the following documents:

- International Conference on Harmonisation (ICH) E9 guideline entitled, “Guidance for Industry: Statistical Principles for Clinical Trials” (**ICH Guideline E9 1998**)
- ICH E3 guideline entitled, “Guidance for Industry: Structure and Content of Clinical Study Reports” (**ICH Guideline E3 1995**)
- Case report forms (eCRF) final version 4.0 (dated 11 October 2013).
- Biostatistical Addendum – Subject Randomization List version 1.0 (02 May 2013).

3.1 Revision History

Version	Date of Revision	Revision
2.0	27 May 2014	
• Section 11.1 Major protocol deviations:
◦ CO breath test >10 ppm on Day 1 is not considered as a major protocol deviation for subjects in the SA arm.
1.0	28 November 2013	Original SAP

4 ABBREVIATION OF TERMS

The following abbreviations are used within this SAP.

1-NA	1-aminonaphthalene
1-OHP	Total 1-hydroxypyrene
2-NA	2-aminonaphthalene
3-HPMA	3-hydroxypropylmercapturic acid
4-ABP	4-aminobiphenyl
11-DTX-B2	11-dehydro-thromboxane B2
ADaM	Analysis Data Model
AE/SAE	Adverse Event/ Serious Adverse Event
ANCOVA	Analysis of Covariance
ANOVA	Analysis of Variance
ATC	Anatomical Therapeutic and Chemical
AUC _{0-24 h}	The area under the curve from 0 to 24 hours
AUQ	Above upper limit of quantification
B[a]P	3-hydroxybenzo(a)pyrene
BMI	Body Mass Index
BoExp	Biomarkers of exposure
CAF	Caffeine
C _{avg}	Weighted average concentration of nicotine or cotinine over 24 hours
CC	Conventional Cigarettes
CEMA	2-cyanoethylmercapturic acid
CI	Confidence Interval
CO	Carbon Monoxide
COHb	Carboxyhaemoglobin
C _{peak}	Peak nicotine or cotinine plasma concentration
CSR	Clinical Study Report
CTCAE	Common Terminology Criteria for Adverse Events and Common Toxicity Criteria
CV	Coefficient of Variation

CYP1A2	Cytochrome P450 1A2
CYP2A6	Cytochrome P450 2A6
ECG	Electrocardiogram
EOS	End of Study
FAS	Full Analysis Set
FEV ₁	Forced Expiratory Volume in 1 second
FTND	Fagerström Test for Nicotine Dependence
FVC	Forced Vital Capacity
glm	General Linear Model
HEMA	2-hydroxyethyl mercapturic acid
HIV	Human Immunodeficiency Virus
HMPMA	3-hydroxy-1-methylpropyl-mercapturic acid
HST	Human Smoking Topography
ICF	Informed Consent Form
ICH	International Conference on Harmonisation
ISO	International Organization for Standardization
IXRS	Interactive Web Response System
LLOQ	Lower Limit of Quantification
LS	Least Squares
MCEQ	Modified Cigarette Evaluation Questionnaire
MedDRA	Medical Dictionary for Regulatory Activities
MHBMA	Monohydroxybutenyl mercapturic acid
MNWS	Minnesota Nicotine Withdrawal Scale
MR	Mean Ratio
NEQ	Nicotine Equivalents
NNAL	4-(methylnitrosamino)-1-(3-pyridyl)-1-butanol
NNN	Total N-nitrosonornicotine
NSAIDS	nonsteroidal anti-inflammatory drugs
o-tol	O-toluidine
PI	Principal Investigator
PK	Pharmacokinetic

PP	Per-Protocol
PT	Preferred Term
PX	Paraxanthine
QC	Quality Control
QSU-brief	Urge-to-Smoke Questionnaire of Smoking Urges Brief
QTcB	QT Interval Corrected using Bazett's Formula
QTcF	QT Interval Corrected using Fridericia's Formula
SA	Smoking Abstinence
SAP	Statistical Analysis Plan
SD	Standard Deviation
SDTM	Standard Data Tabulation Module
SMAR	Smoking article
SOC	System Organ Class
SOP	Standard Operating Procedure
S-BMA	S-benzylmercapturic acid
S-PMA	S-phenylmercapturic acid
THS	Tobacco Heating System
TFL	Tables, Figures, and Listings
t_{peak}	Time to peak concentration
ULOQ	Upper Limit of Quantification
UV	Ultra violet
VAS	Visual Analogue Scale
WHO	World Health Organisation
YG1024+S9	Ames Mutagenicity Test

The following special terms are used in this SAP:

Baseline period	06:30 AM at Day -1 until 06:29 AM of Day 1 (and prior to product use /CC consumption on Day 1 if randomized to THS 2.2 or CC arm).
Conventional cigarette (CC)	The term 'conventional cigarette' refers to manufactured and commercially available cigarettes and excludes hand-rolled cigarettes, cigars, pipes, bidis, and other nicotine-containing products.
CC incompatible with Human Smoking Topography (HST) device	All CCs that are incompatible with the HST device (e.g., slim CC).
Day of Discharge	Day 6
Enrolment	On Day -2 for eligible subjects after all applicable inclusion and exclusion criteria have been satisfactorily met and the subject is willing and ready to use THS 2.2 (the test of THS 2.2 is the last assessment prior to enrolment).
Exposure period	06:30 AM of Day 1 until 11:00 PM of Day 5
Randomization	Assignment of the subject randomization number in the Interactive Web and Voice Response System (IXRS). This can be done any time on Day 0, however, subjects are not informed of their randomization group and number prior to Day 1.
Run-in period	Admission to site until 06:29 AM of Day -1
Safety follow-up	After the time of Discharge, a 7-day safety follow-up will be done for the recording of spontaneously reported new AEs/SAEs and the active follow-up of ongoing AEs/SAEs by the site.
Screening failure	Subjects who are not enrolled will be considered a screening failure and will be replaced by other subjects.
Tobacco Heating System 2.2 (THS 2.2)	THS 2.2 is comprised of the following components: Tobacco Stick, Holder, Charger, a Cleaning Tool, a mains power supply, and a USB cable.

5 STUDY OBJECTIVES AND ENDPOINTS

5.1 Primary Objective and Endpoints

1. To demonstrate the reduction of primary biomarkers of exposure (BoExp) in smokers switching from CC to THS 2.2 as compared to smokers continuing to smoke CC.

Endpoints:

- Monohydroxybutenyl mercapturic acid (MHBMA) 24-hour urine concentration adjusted for creatinine on Day 5.
- 3-hydroxypropylmercapturic acid (3-HPMA) 24-hour urine concentration adjusted for creatinine on Day 5.
- S-phenylmercapturic acid (S-PMA) 24-hour urine concentration adjusted for creatinine on Day 5.
- Carboxyhemoglobin (COHb) in blood (expressed as % saturation of hemoglobin) as measured on Day 5.

5.2 Secondary Objectives and Endpoints

1. To determine the reduction of secondary BoExp on Day 5 in smokers switching from CC to THS 2.2 as compared to smokers continuing to smoke CC.

Endpoints:

- Quantity Excreted in urine over 24 hours for MHBMA, S-PMA and 3-HPMA.
- Carbon monoxide (CO) (expressed as ppm) in exhaled breath.
- Urinary BoExp (expressed as quantity excreted and concentration adjusted for creatinine) in 24-hour urine:
 - Total 1-hydroxypyrene (1-OHP),
 - Total N-nitrosodimethylamine (NNN),
 - 4-aminobiphenyl (4-ABP),
 - 1-aminonaphthalene (1-NA),
 - 2-aminonaphthalene (2-NA).
 - o-toluidine (o-tol).
 - 2-cyanoethylmercapturic acid (CEMA).
 - 2-hydroxyethyl mercapturic acid (HEMA).
 - 3-hydroxybenzo(a)pyrene (B[a]P).
 - 3-hydroxy-1-methylpropyl-mercapturic acid (HMPMA).
 - S-benzylmercapturic acid (S-BMA).
 - Total 4-(methylnitrosamino)-1-(3-pyridyl)-1-butanol (total NNAL).

2. To describe the levels of primary and secondary BoExp over the exposure period in smokers switching from CC to THS 2.2 as compared to smokers continuing to smoke CC.

Endpoints:

- CO (expressed as ppm) in exhaled breath.

- COHb in blood (expressed as % saturation of Hemoglobin).
- Urinary BoExp (expressed as quantity excreted and concentration adjusted for creatinine) in 24-hour urine:
 - MHBMA.
 - 3-HPMA.
 - S-PMA.
 - 1-OHP.
 - Total NNN.
 - 4-ABP.
 - 1-NA.
 - 2-NA.
 - o-tol.
 - CEMA.
 - HEMA.
 - B[a]P.
 - HMPMA.
 - S-BMA.
 - Total NNAL.

3. To determine the levels of nicotine on Day 5 in smokers switching from CC to THS 2.2 as compared to smokers continuing to smoke CC and to describe their levels over the exposure period from Day 1 to Day 5.

Endpoints:

- Nicotine equivalents (NEQ) (expressed in quantity excreted and concentration adjusted for creatinine) in 24-hour urine on Day 5 and from Day 1 to Day 5.
- Plasma nicotine and cotinine concentrations.

4. To describe the levels of primary, secondary BoExp and BoExp to nicotine over the exposure period in smokers switching from CC to THS 2.2 as compared to smokers switching from CC to smoking abstinence (SA).

Endpoints:

- COHb in blood (expressed as % saturation of hemoglobin).
- CO (expressed as ppm) in exhaled breath.
- Urinary BoExp (expressed as quantity excreted and concentration adjusted for creatinine) in 24-hour urine:
 - MHBMA.
 - 3-HPMA.
 - 3-S-PMA.
 - 1-OHP.
 - Total NNN.
 - 4-ABP.
 - 1-NA.
 - 2-NA.
 - o-tol.
 - CEMA.
 - HEMA.
 - B[a]P.
 - HMPMA.
 - S-BMA.
 - Total NNAL.
 - NEQ.

5. To describe the pharmacokinetic (PK) profiles of the nicotine and cotinine in smokers switching from CC to THS 2.2 as compared to smokers continuing to smoke CC.

Endpoints:

- Peak (highest concentration value along the day) on Day 5 in plasma.

- Time to peak (actual time when the peak was observed compared to the time of the first cigarette) on Day 5.
- Weighted average concentration over 24 hours on Day 5.

6. To describe the changes in Cytochrome P450 1A2 (CYP1A2) enzymatic activity on Day 5 in smokers switching from CC to THS 2.2, switching from CC to SA, and continuing to smoke CC.

Endpoints:

- Molar metabolic ratio of paraxanthine (PX)/caffeine (CAF) in plasma on Day 5.

7. To describe the daily THS Tobacco Stick/CC consumption over the exposure period in smokers switching from CC to THS 2.2 as compared to smokers continuing to smoke CC.

Endpoints:

- Number of THS Tobacco Sticks and CC used each day for each subject from Day -1 to Day 5.

8. To monitor the safety profile during the study.

Endpoints:

- Incidence of adverse events (AEs)/serious adverse events (SAEs) and device events, including THS 2.2 malfunction/misuse.
- Respiratory symptoms: cough assessment by visual analogue scale (VAS), Likert scales, and one open question.
- Vital signs.
- Spirometry.
- Electrocardiogram (ECG).
- Clinical chemistry, hematology, and urine analysis safety panel.
- Physical examination.
- Concomitant medications.

5.3 Exploratory Objectives and Endpoints

1. To describe the following parameters in smokers switching from CC to THS 2.2 as compared to smokers continuing to smoke CC and smokers switching from CC to SA:

Endpoints:

- Ames Mutagenicity test (YG1024+S9).
- The total score, factor 1 (relief) and factor 2 (reward) from Questionnaire of Smoking Urges (brief version) [QSU-brief] (Cox et al. 2001)
- The total scores from Minnesota Nicotine Withdrawal Scale (MNWS) (Hughes and Hatsukami 2008).

- CYP2A6 enzymatic activity as molar ratio of 3-hydroxycotinine and cotinine
- Selected risk markers (expressed as quantity excreted and concentration adjusted for creatinine) in 24-hour urine:
 - 8-epi-prostaglandine F2 α (8-epi-PGF2 α)
 - 11-dehydro-thromboxane B2 (11-DTX-B2)

2. To evaluate in smokers switching from CC to THS 2.2, and smokers continuing smoking CC and smokers switching from CC to SA the relationship between¹:

Endpoints:

- Primary and secondary BoExp and NEQ:
- NEQ in urine by:

– Blood COHb.	– 2-NA in urine.
– MHBMA in urine.	– o-tol in urine.
– 3-HPMA in urine.	– CEMA in urine.
– S-PMA in urine.	– HEMA in urine.
– Exhaled CO.	– B[a]P in urine.
– 1-OHP in urine.	– HMPMA in urine.
– Total NNN in urine.	– S-BMA in urine.
– 4-ABP in urine.	– Total NNAL in urine.
– 1-NA in urine.	

¹ The reporting of this objective will be the subject of a separate report.

- Selected risk markers and NEQ² :
- NEQ in urine by:
 - 8-epi-PGF2α in urine
 - 11-DTX-B2 in urine

All biomarkers measured in urine will be expressed as quantity excreted and concentration adjusted for creatinine in 24-hour urine.

3. To describe the following parameters over the course of the study in smokers switching from CC to THS 2.2 as compared to smokers continuing smoking CC:

Endpoints:

- The subscales from the Modified Cigarette Evaluation Questionnaire (MCEQ) (Cappelleri et al. 2007).
- The following parameters measured per cigarette from the human smoking topography (HST) device.
 - Total number of puffs.
 - Total puff volume.
 - Average puff volume.
 - Average puff duration.
 - Total puff duration.
 - Average flow.
 - Average Peak flow.
 - Total inter puff interval.
 - Average inter puff interval.
 - Total smoking duration.
 - Total work.
 - Average work.
 - Average pressure drop.
 - Average peak pressure drop.
 - Smoking intensity.
 - Puffing time index.
 - Puff frequency.
 - HST questionnaire.

4. To describe the following parameters over the course of the study in smokers switching from CC to THS 2.2:

Endpoints:

- Potential combustion occurrences in tobacco plugs: visual inspection of the tobacco plugs.
- Filter analysis: smoke nicotine in filter and ultra violet (UV) absorbance at 310 nm.

5.4 Additional Endpoints

The following additional safety assessments will be made:

- Serology for human immunodeficiency virus (HIV) 1/2 and Hepatitis B and C
- Urine pregnancy test (females only), urine cotinine test, urine drug screen
- Alcohol breath test
- Chest X-ray

² This objective has changed from the protocol, see Section 9, 'Changes from the Protocol Specified Statistical Analysis'.

- Nicotine dependence to be assessed with the Fagerström Test for Nicotine Dependence (FTND) revised version (**Fagerström et al. 2012**)

5.5 Study Hypotheses And Evaluation Criteria

5.5.1 Hypotheses

The hypothesis to be tested for each of the primary and secondary BoExp is that the geometric mean level on Day 5 of the BoExp for THS 2.2 is lower relative to CC.

5.5.2 Evaluation Criteria

The study will be considered successful if the study demonstrates a 50% or more reduction in MHBMA, 3-HPMA, S-PMA, and COHb in the THS 2.2 arm compared to the CC arm (as measured on Day 5), using a one-sided test with 2.5% type I error probability.

6 INVESTIGATIONAL PLAN

6.1 Study Design

This is a randomized, controlled, open-label, 3-arm parallel group, single-center study, stratified randomization by sex and average daily CC consumption over the last 4 weeks as reported during the Screening Visit (10 - 19 CC/day vs. >19 CC/day). (**Figure 1** “Study Flowchart”).

In total, 160 eligible, healthy smoking subjects will be randomized into one of the three study arms in **Table 1 “Definition of Study Arms”**.

Table 1 Definition of Study Arms

Study arm	Number of subjects
THS 2.2	80
CC	40
Smoking abstinence	40

This is an *ad libitum* smoking study. In general, smoking during confinement will be allowed between 06:30 AM and 11:00 PM.

The Screening Visit will be conducted within 4 weeks prior to Admission to the investigational site (Day -30 to Day -3). Screening procedures do not necessarily have to be conducted on the same day. During the Screening Visit the site staff will demonstrate the use of THS 2.2.

Subjects will be admitted to the clinical site on Day -2 (Admission). At Admission, in female subjects, the urine pregnancy test must be negative before the product test of THS 2.2 is performed. The THS 2.2 product test, (use of up to 3 THS Tobacco Sticks) is the last procedure of the eligibility assessments, prior to enrolment. After the inclusion and

exclusion criteria have been satisfactorily met, only subjects willing and able to use THS 2.2 will be enrolled in the study, to minimize the drop-out rate during the course of the study.

Subjects are enrolled on Day -2, and then randomized on Day 0. From Day-2 to Day 0, all subjects will continue smoking their single preferred brand of CC and baseline values will be recorded on Day -1 and Day 0. On Day 0, subjects will be randomized to 1 of the 3 study arms (see **Table 1 “Definition of Study Arms”**). Subjects will be informed of their randomized study arm by the study site staff on Day 1 prior to 06:30 AM.

[figure not shown]
The exposure period (from Day 1, 06:30 AM to Day 5, 11:00 PM) will consist of 5 days of *ad libitum* use of the assigned product between 06:30 AM and 11:00 PM each day (THS 2.2 and CC arms). Use of any tobacco/nicotine containing product other than the assigned product will not be allowed and may, at the discretion of the Principal Investigator (PI) or designee, result in the subject's withdrawal from the study.

Subjects in the SA arm will be asked to abstain from smoking any nicotine/tobacco containing product and will not be provided with medication to support SA. Subjects will be provided with psychological support during the period of smoking abstinence.

The end of the 24-hour urine collection period for Day 5 will end in the morning on Day 6 prior to Discharge.

Subjects will be discharged from the investigational site in the morning of Day 6 after all safety examinations of the Day of Discharge have been conducted. Use of CC will be allowed on Day 6, but only after spirometry has been performed.

After Discharge, subjects will enter into a 7-day safety follow-up to capture spontaneously reported new AEs/SAEs and for active follow-up of ongoing AEs/SAEs. Any AE will in general be followed up until resolved, stabilized (i.e., no worsening of the event), or until a plausible explanation for the event has been found. The end of study (EOS) is defined as the end of the 7-day safety follow-up period.

**Figure 1 Study Flowchart**

Abbreviations: THS 2.2 = Tobacco Heating System 2.2; CC = conventional cigarettes.

6.1.1 Timing of Confinement Period

The 9 day confinement period consists of:

- The Admission Day (Day -2).
- The run-in period, from Admission on Day -2 until 06:29 AM of Day -1.
- The baseline period, from Day -1, 06:30 AM until Day 1, 06:29 AM.
- The exposure period, from Day 1 06:30 AM until Day 5, 11:00 PM.
- The day of Discharge, Day 6, from Day 5, 11:01 PM to time of Discharge.

6.2 Selection of Study Population

6.2.1 Inclusion Criteria

The following inclusion criteria will be applicable for this study:

1. Subject has signed the informed consent form (ICF) and is able to understand the information provided in the Subject Information Sheet and ICF.
2. Subject is aged from 21 to 65 years (inclusive).
3. Subject is Caucasian.
4. Smoking, but healthy subject as judged by the PI or designee based on all available assessments from the Screening period/Day of Admission

5. Subject is a current smoker (based on self-reporting), who for the last 4 weeks has smoked at least 10 commercially available non-menthol CCs/day (no brand restrictions) with a maximum yield of 1 mg nicotine International Organization for Standardization (ISO) per cigarette, as labeled on the cigarette package. Furthermore, the subject has smoked for at least the last 3 consecutive years.
6. Subject does not plan to quit smoking in the next 3 months.
7. The subject is ready to accept 5 days of SA.
8. The subject is ready to accept using the THS 2.2 product.

6.2.2 Exclusion Criteria

The exclusion criteria are:

1. As per PI or designee judgment, the subject cannot participate in the study for any reason.
2. A subject who is legally incompetent, physically or mentally incapable of giving consent.
3. The subject has medical condition requiring smoking cessation, or clinically relevant diseases in the judgment of the PI or designee.
4. The subject has a body mass index (BMI) <18.5 or $\geq 32.0 \text{ kg/m}^2$.
5. Medical conditions which require or will require in the course of the study a medical intervention which may interfere with the study participation and/or study results.
6. The subject has used nicotine-containing products other than commercially available CC (either tobacco-based products or nicotine-replacement therapy) as well as electronic cigarettes and similar devices, within 4 weeks prior to assessment.
7. The subject has received medication within 14 days or within 5 half-lives of the drug prior to the Admission Day which has an impact on CYP1A2 or CYP2A6 activity.
8. If a subject received any medication (prescribed or over the counter) within 14 days prior to Screening or prior to the Admission Day it will be decided at the discretion of the PI or designee if these can potentially interfere with the study objectives and subject's safety.
9. Concomitant use of nonsteroidal anti-inflammatory drugs (NSAIDS) or acetylsalicylic acid.
10. The subject has a positive alcohol test and/or the subject has a history of alcohol abuse that could interfere with subject's participation in the study.
11. The subject has a positive urine drug test.
12. Positive serology test for human immunodeficiency virus (HIV) 1/2, hepatitis B surface antigen or hepatitis C virus.
13. Donation or receipt of whole blood or blood products within 3 months prior to Admission.
14. The subject is a former or current employee of the tobacco industry or of their first-degree relatives (parent, sibling or child).
15. The subject is an employee of the investigational site or any other parties involved in the study or of their first-degree relatives (parent, sibling or child).

16. The subject has participated in a clinical study within 3 months prior to the Screening Visit.
17. The subject has previously participated in the same study at a different time (i.e., each subject can be included in the study population only once).
18. For women only: Subject is pregnant (does not have negative pregnancy tests at Screening and at Admission), or is breast feeding.
19. For women only: Subject does not agree to use an acceptable method of contraception*.

* Intrauterine device, intrauterine system, barrier methods of contraception (condoms, occlusive caps) with spermicidal foam/gel/film/suppository, hormonal contraception containing progesterone only, vasectomized partner(s) or true abstinence (periodic abstinence and withdrawal are not effective methods) from Screening until the end of the safety follow-up period. Hormonal contraception with oestrogen containing products is NOT allowed in this study.

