| 7. The subject has received medication (prescription or over-the-counter) within 14 days or within 5 half-lives of the drug (whichever is longer) prior to the Admission Day (Day -2), which has an impact on CYP1A2 or CYP2A6 activity. | Effect | | X |
| 8. If a subject has received any medication (prescribed or over-the-counter) within 14 days prior to Screening or prior to the Admission Day (Day -2), it will be decided at the discretion of the Investigator or designee if these can potentially interfere with the study objectives or subject's safety. | Effect | X | X |
| 9. Concomitant use of nonsteroidal anti-inflammatory drugs (NSAIDs) or acetylsalicylic acid. | Effect | X | X |
| 10. The subject has a positive alcohol test and/or the subject has a history of alcohol abuse that could interfere | Administrative | X | X |

Confidentiality statement: Data and information contained in this document are considered to constitute trade secrets and confidential commercial information, and the legal protections provided to such trade secrets and confidential information are hereby claimed under the applicable provisions of applicable law. No part of this document may be publicly disclosed without the written consent of Philip Morris Products S.A.

| Exclusion Criteria | Rationale | Screening | Day of Admission (Day -2) |
|---|------------------|------------------|----------------------------------|
| with the subject's participation in the study. | | | |
| 11. The subject has a positive urine drug test. | Administrative | X | X |
| 12. Positive serology test for human immunodeficiency virus (HIV)1/2, hepatitis B surface antigen (HbsAg), or hepatitis C virus (HCV). | Safety | X | |
| 13. Donation or receipt of whole blood or blood products within 3 months prior to Admission. | Safety | X | X |
| 14. The subject is a current or former employee of the tobacco industry or of their first-degree relatives (parent, sibling, or child). | Administrative | X | |
| 15. The subject is an employee of the investigational site or any other parties involved in the study or of their first-degree relatives (parent, sibling, or child). | Administrative | X | |
| 16. The subject has participated in a clinical study within 3 months prior to the Screening Visit. | Safety | X | |
| 17. The subject has previously participated in the same study at a different time (i.e., each subject can be included in the study population only once). | Administrative | X | |

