| 18. For women only: Subject is pregnant (does not have negative pregnancy tests at Screening and at Admission) or is breast feeding. | Safety | X | X |

Confidentiality statement: Data and information contained in this document are considered to constitute trade secrets and confidential commercial information, and the legal protections provided to such trade secrets and confidential information are hereby claimed under the applicable provisions of applicable law. No part of this document may be publicly disclosed without the written consent of Philip Morris Products S.A.

| Exclusion Criteria | Rationale | Screening | Day of Admission (Day -2) |
|--|-----------|-----------|------------------------------|
| 19. For women only: Subject does not agree to use an acceptable method of effective contraception.* | Safety | X | X |

* Intrauterine device, intrauterine system, established use of oral/injectable/implantable/transdermal hormonal methods, barrier methods of contraception (condoms, occlusive caps) with spermicidal foam/gel/film/suppository, vasectomized partner(s), or true abstinence (periodic abstinence and withdrawal are not effective methods) from Screening until the end of the safety follow-up period.

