Estrogens for contraception and for hormone replacement therapy, even though known to be CYP1A2 inhibitors, will be allowed in this study. The use of estrogens must be documented on the eCRF.

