**Table 2. Examples of Medications with Effects on CYP1A2 and CYP2A6 Activity**

| Drug name | Substance Class |
|--|--|
| Fluoroquinolones, including ciprofloxacin and ofloxacin, nafcillin, rifampicin | Antibiotic |
| Fluvoxamine, fluoxetine, paroxetine, bupropion, duloxetine, amitriptyline, imipramine, sertraline, mirtazapine, citalopram, thioridazine | Antidepressant |
| Haloperidol, perphenazine, chlorpromazine, propoxyphene fluphenazine, clozapine, olanzapine | Neuroleptic |
| Phenobarbital, primidone, carbamazepine | Antiepileptic |
| Cholorquine, quinidine | Antirheumatic |
| Clotrimazole, terbinafine, fluconazole, ketoconazole, miconazole | Antimycotic |
| Erythromycin, ciprofloxacin, clarithromycin, norfloxacin | Antibiotic |
| Cimetidine, chlorpheniramine, diphenhydramine, ranitidine | H2-receptor antagonist |
| Amiodarone, verapamil, mibefradil, mexiletin, propafenone, propranolol, lidocaine | Antiarrhythmic |
| Losartan, amlodipine, nifedipine, losartan | Antihypertensive |
| Drosperinone, estrogens | Hormonal contraceptives, Agents for hormonal replacement therapy (estrogens) |
| Fluvastatin | Cholesterol-lowering agent |
| Theophylline | Antispasmodic pulmonological agent/Bronchodilator agent |
| Omeprazole, lansoprazole | Proton pump inhibitor |
| Interferon | Antiviral/Immunomodulating agent |
| Methoxsalen | Anti-psoriatic (substance class Furocoumarins) |
| Modafinil, diclofenac, rofecoxib | Analgesic |
| Insulin | Anti-diabetic |
| Sildenafil | Phosphodiesterase-Inhibitor (e.g., used for treatment of Erectile dysfunction) |

Confidentiality statement: Data and information contained in this document are considered to constitute trade secrets and confidential commercial information, and the legal protections provided to such trade secrets and confidential information are hereby claimed under the applicable provisions of applicable law. No part of this document may be publicly disclosed without the written consent of Philip Morris Products S.A.

| | |
|-----------------|---|
| Quinine | Crystalline alkaloid |
| St. John's Wort | Over-the-counter (herbal remedy) antidepressant |
| Psoralen | Anti-psoriatic (substance class Furocoumarins) |
| Pilocapine | Cholinergic agonists (e.g., used for Glaucoma Therapy) |

Data sources: Chang and Kam, 1999; Ingelman-Sundberg et al, 1999; Lacy et al, 2007. The list is not exhaustive.

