11.1 Major Protocol Deviations

Subjects with major protocol deviations will be identified (at a population level) to determine whether they will be excluded from any analysis population. This will take place during the pre-analysis data review meeting prior to database lock. The following have been identified as the major protocol deviations.

The categories for the major deviations will include, but are not limited to the deviations presented in Table 14.

Table 14: Definition of Major Protocol Deviations

Category	Description
Mis-randomization	Being administered the wrong product according to the randomization schedule.
	Use of any nicotine or tobacco-containing product other than the assigned product.
Product compliance	Exhaled CO breath test >10 ppm for subjects from the SA arm after Day 2
Violation	Violation of inclusion/exclusion criteria.
Duration of 24 hour collection	Start and end times not within the 30 min window.

Among the above criteria, violations of inclusion criteria 5 to 7, or of the exclusion criteria 1, 3 to 16, and 18 will be assessed for their impact on the PP Population and evaluated during the pre-analysis data review meeting (Section 6.3.1 “Methods of Assigning Subjects to Product Arms”).

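### The SAP bars oestrogen-containing contraception that the protocol allows, so compliant women could be misclassified as major deviators, and the CYP1A2 model makes no provision for recorded oestrogen use

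*SAP*

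**What the plan says.** **Eligibility.** Protocol section 6.7 states: "Estrogens for contraception and for hormone replacement therapy, even though known to be CYP1A2 inhibitors, will be allowed in this study". It adds: "The use of estrogens must be documented on the eCRF". The footnote to exclusion criterion 19 in protocol section 5.1.2 counts "established use of oral/injectable/implantable/transdermal hormonal methods" among the acceptable methods, with no limit on oestrogen content. The SAP's version of the same footnote (section 6.2.2) accepts "hormonal contraception containing progesterone only" and then says "Hormonal contraception with oestrogen containing products is NOT allowed in this study".

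**Medication affecting CYP1A2 or CYP2A6.** Exclusion criterion 7 in the protocol bars recent medication "which has an impact on CYP1A2 or CYP2A6 activity", and protocol Table 2 lists "Drosperinone, estrogens" among the examples. The exception for oestrogens stands only in section 6.7. The SAP restates criterion 7 and does not carry the exception.

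**Deviations.** SAP Table 14 (section 11.1) lists "Violation of inclusion/exclusion criteria" as a major deviation. Section 11.1 then names, by number, the criteria whose violation is to be assessed for the per-protocol (PP) population: among the exclusions these are 1, 3 to 16, and 18. Number 7 is in the list and number 19 is not.

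**CYP1A2.** SAP section 12.6.2.4 compares Day 5 activity in an ANOVA with sex, daily cigarette consumption and product. There is no term for oestrogen use and none for the Day 0 value.

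**The concern.** The two documents give opposite rules under the same criterion number. Versioning does not explain it: the SAP says it supplements the protocol dated 25 April 2013, which is the version supplied. SAP section 9 records changes as small as a preposition in the creatinine wording but not this one, and the only change logged for SAP version 2.0 concerns the CO breath test in the abstinence arm.

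Two things are at stake. First, the same woman can be compliant or a major deviator depending on which list is used, so the deviation table and the eligibility listing may be inconsistent, and PP membership may be questioned. Second, the protocol itself calls oestrogens CYP1A2 inhibitors and requires their use to be recorded, yet the analysis of CYP1A2 activity, a secondary endpoint, has no rule for using that information.

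**Working it through.** The plan states no figure on this point, so there is none to reproduce. The check is a reading of the rules, followed by a scale calculation on assumed prevalence.

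**Step 1. How one woman using an oestrogen-containing contraceptive, as the protocol allows, would be classified**

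| Rule applied | Result |
|---|---|
| Protocol 6.7 and footnote 19, with SAP section 11 (deviations measured against the protocol) | No deviation |
| SAP criterion 19 with SAP Table 14 | Major deviation, not on the list for PP assessment |
| Criterion 7 as written, protocol Table 2, SAP Table 14 | Major deviation, on the list for PP assessment |

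SAP Table 15 adds a minor category for drugs affecting CYP2A6 only. Protocol Table 2 does not say which enzyme each drug affects, so it does not settle whether oestrogens belong there. A woman taking oestrogen as hormone replacement therapy is not touched by the SAP's criterion 19, which concerns contraception, but the criterion 7 route would still reach her.

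**Step 2. How many women**

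Each sex must be at least 40% of 160 subjects. Minimum women: 0.40 × 160 = 64. Maximum: 160 − 64 = 96. The documents give no prevalence of oestrogen use, so it is assumed over a range:

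| Assumed share of women | Users, 64 women | Users, 96 women |
|---|---|---|
| 5% | 3.2 | 4.8 |
| 10% | 6.4 | 9.6 |
| 20% | 12.8 | 19.2 |
| 30% | 19.2 | 28.8 |
| 50% | 32.0 | 48.0 |

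SAP section 10 runs the PP analysis only if more than 10 subjects are excluded from that set. Eleven users is 11/64 = 17.2% of 64 women, or 11/96 = 11.5% of 96. This would matter only if the review actually excluded them.

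**Step 3. What is at risk in the CYP1A2 contrast**

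Randomisation is 2:1:1 within sex strata, so 64 women split about 32:16:16 and 96 women about 48:24:24. With a share p of women using oestrogen, the standard deviation of the THS-minus-CC difference in that share is √[p(1−p)(1/n₁ + 1/n₂)].

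- 64 women, p = 0.10: √(0.09 × 0.09375) = 0.092
- 64 women, p = 0.30: √(0.21 × 0.09375) = 0.140
- 96 women, p = 0.10: √(0.09 × 0.0625) = 0.075
- 96 women, p = 0.30: √(0.21 × 0.0625) = 0.115

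Chance differences of roughly 8 to 14 percentage points among women are therefore ordinary. To translate this, suppose oestrogen shifts the ratio by s = 1 SD (an assumption). A one-SD imbalance then moves the overall contrast by the female share × imbalance × s: 0.40 × 0.140 = 0.056 SD, or 0.60 × 0.115 = 0.069 SD. The standard error of the contrast is √(1/80 + 1/40) = 0.194 SD, so the movement is about 0.29 to 0.36 of a standard error.

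The same effect seen as added variance is √[1 + f·p(1−p)·s²], with f the female share. For f from 0.4 to 0.6, p from 0.10 to 0.30 and s from 0.5 to 1.0, it runs from 1.004 to 1.061, an increase in SD of 0.4% to 6.1%.

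**The case against.** The strongest reply is that nothing goes wrong if the SAP is read as a whole. Section 11 measures deviations against the protocol, section 6.2 only restates the criteria and often shortens them, and deviations are reviewed before anyone leaves the PP set. A woman who meets the protocol's criterion 19 has not deviated from it. On CYP1A2, the objective is descriptive and the endpoint is outside the success criterion. Randomisation is stratified by sex and the model includes sex, so any imbalance in use established before randomisation arises by chance, which the confidence interval already reflects. Stable use is also present on Day 0, so the planned percent-change summary takes account of part of it.

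Most of this stands, and it rules out three stronger readings that a reader might infer:

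- *Every compliant user will be recorded as a major deviator.* Section 11 points the other way; misclassification is possible, not certain.
- *An imbalance would go unseen.* Oestrogen use is on the eCRF, concomitant medications are tabulated by actual exposure (SAP section 12.6.4.5.1), and protocol section 6.7 requires a review of medication for CYP1A2 impact before database lock.
- *The CYP1A2 comparison is systematically biased.* Only chance imbalance is possible.

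The reply does not remove the contradiction. The SAP prints its own criteria, refers to them by number in section 11.1 and lists whether each was met, so anyone programming from it has the opposite rule in hand. Nor does the SAP turn the protocol's pre-lock medication review into an analysis rule for CYP1A2.

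**Conclusion.** The point holds in limited form. There is a direct, undeclared contradiction between the SAP's criterion 19 and the protocol, which could cause compliant women to be classed as major deviators. Criterion 19 itself does not lead to PP assessment; criterion 7 could, because its oestrogen exception sits in another protocol section that the SAP does not repeat.

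The reach is restricted. The PP population serves only as a robustness check on the primary endpoint, and the CYP1A2 analysis uses the full analysis set. A reader might infer that the primary conclusion is in doubt; it is not, because the primary analysis is on the full analysis set and does not depend on how these women are classified.

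For CYP1A2 the gap is a missing pre-specification with a modest expected effect: a typical chance shift of up to about a third of a standard error at the upper end of the assumed range (30% of women using oestrogen, a 1 SD effect). Neither the prevalence nor the effect size is in the documents. If few or no users were enrolled, this part lapses.

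**What to change.** 1. Before deviations are classified, reconcile SAP section 6.2.2 (criteria 7 and 19) with protocol section 5.1.2 (criteria 7 and 19), section 6.7 and Table 2. Which eligibility rule is right is for the sponsor and the investigator to settle; this review takes no position.
2. State in SAP section 11 which document's criteria define an eligibility deviation, and how recorded oestrogen use is treated under criterion 7. Record any intended change in SAP section 9.
3. If oestrogen users are enrolled, pre-specify one supportive sensitivity analysis of Day 5 CYP1A2 activity, adding recorded oestrogen use (yes/no) as a covariate to the planned model. The Day 0 value could be added in the same run, since it would absorb whatever part of the effect is stable.

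The cost is wording in the SAP, the protocol or both, plus one model run on data already collected on the eCRF.
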